Upon completing the informed consent process, interested participants will be asked to sign or fingerprint a copy of the written informed consent to confirm that they understand the study and what is expected of them as a research participant. A copy of the signed consent form will be given to the participant for their records. After signing of the consent, participants will be considered enrolled as part of the sample goal of 150 uninfected women.

Enrolled women will participate in the outlined mixed-method study to evaluate prevalence and determinants of uptake and adherence (tenofovir plasma concentration >40ng/mL, taking >80% of dispensed pills) to daily, oral TDF/FTC PrEP during periconception among HIV uninfected Ugandan women reporting HIV-infected or unknown serostatus partners. To accomplish this, women will participate in quarterly study visits, HIV and pregnancy testing, questionnaires and safer conception/adherence group counseling sessions. Participants will be eligible to initiate PrEP at any time during the first 6 months of the 9-month (maximum) study follow-up period. Participants will receive a PrEP referral form to bring to the clinic if they chose to initiate PrEP outside of a scheduled study follow up visit.

Women who become pregnant or test positive for HIV during the 9-month follow-up period will complete exit activities (questionnaire and in-depth interview) and be referred to appropriate antenatal and/or HIV follow-up care.

Counseling

Comprehensive safer conception counselling: Enrolled women will be offered a package of safer conception counselling for uninfected women who want to conceive a child with an infected partner:

- Encourage partner testing and serostatus disclosure within the partnership.
- Encourage partner to initiate ART if he is eligible by national guidelines (CD4 cell count \leq 500 or in serodiscordant partnership),
- Delay sex without condoms until he achieves HIV viral load suppression or is on ART x 6 months,
- Consider contraception to delay pregnancy until safer conception strategies implemented
- Limit sex without condoms to peak fertility, and / or
- Consider sperm washing, donor sperm, and adoption as alternatives.

Safer conception counselling will occur at baseline and then quarterly thereafter in non-pregnant women

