Adherence support counselling: Brief adherence counselling and support sessions will be available at to all women at the time of enrollment and will cover PrEP education. Follow-up adherence counselling will be available during quarterly visits to all women who initiate PrEP. Counselling will be performed by trained study counsellors in a individual counselling session. These sessions will discuss barriers to and promoters of adherence. **Data Collection (Table 3)**

Demographics: We will collect baseline demographic and reproductive health data (number of prior pregnancies, live births, living children) at enrollment. We will update demographic data at study exit to assess information that may change throughout the course of the study (e.g. employment, household income).

Measures: Constructs will be assessed with a questionnaire administered at 0 months and study exit (Table 2). *Other safer conception behaviors* will also be assessed, including partner HIV status, delay of sex without condoms until partner on ART with viral load suppression, accessing additional services such as sperm washing.

Sexual Behavior: Sexual behavior will be assessed through monthly diaries. The counsellor and the participant will fill in the first day of next anticipated menses on a monthly calendar and then participants will mark the number of condomless sex acts and bring this form back in for review at quarterly follow-up visits. We will use the sexual behavior data of woman who chose not to initiate PrEP to explore between group differences among individuals who chose to and who chose not to initiate PrEP. In addition, we will be able to better understand the entire sample's understanding and use of the alternative/additional safer conception strategy of timing sex to peak fertility by collecting this data regardless of PrEP initiation.

Biologic tests; All participants: All participants will complete quarterly urine pregnancy tests, rapid HIV tests and syndromic screening for STIs.

Beta hcg-urine pregnancy tests require approximately 4 drops of urine to test for human chorionic gonadotropin, a hormone that is produced once a woman becomes pregnant. Women who test positive for pregnancy after enrolment will be referred to appropriate antenatal care before being exited from the study.

Rapid HIV testing will occur via the standard of care finger-prick blood sample. HIV finger-prick testing will entail the clinical study member pricking the tip of the participant's

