Table 3. Data collection procedures					
Months	0	i*	3	6	9/stud exit
Laboratory					
Urine pregnancy test	x		x	x	x
HIV test	x		x	x	x
STI screen	x		x	x	x
STI Objective Testing	x			x	
STI Case Report Form	x			x	
Additional labs for women who initiate PrEP					
Creatinine		x	x	x	x
HBV serology		x			
Drug level adherence testing			x	x	x
Behavioral					
Safer conception counseling	x		x	x	x
Full questionnaire (See Table 2)	x				x
diary sexual behavior	x		x	x	x
Wisepill adherence data	x		x	x	x
In-depth interviews (See Aim 3)				x	x
Additional for women who initiate PrEP					
Adherence support	x	x	x	x	x
*i = PrEP initiation visit					
** Objective STI Testing will include: gonorrhoeae, chlamydia, trichomonas vaginalis, herpes and syphilis at baseline and month 6 for all participants and as needed based on screening at all other visits/exit					

finger with a small, single-use lancet, squeezing a small amount of blood (approximately 1-2 drops) into a sample collection pipette, transferring a drop of blood into a marked sample well and waiting approximately 10-20 minutes for results. Women who test positive will receive a second, confirmatory finger-pick test. Upon completion of confirmatory testing, women who were confirmed positive will receive post-test counselling and be referred for appropriate HIV care before being exited from the study.

Syndromic STI screening: All women will be offered syndromic STI screening at each study visit. Syndromic STI screening will be conducted by asking participants if they have experienced any STI symptoms (e.g. discharge, ulcers, itching). For women who endorse STI symptoms a confirmatory test will be performed, and they will receive treatment medications dispensed by a licensed medical professional team member (see STI treatment below),

Objective STI testing: Women who consent to participate in objective STI testing will complete objective STI screening tests at baseline, at the 6-month study visit or study exit (if exit occurs prior to the 6-month timepoint) independent of the syndromic STI screen (see above).

Women who endorse symptoms of STI, as determined by syndromic STI screening, during interim visits or at the 3-month study visit will have additional objective STI testing.

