STI Treatment: Participants with positive STI testing will receive treatment at the study site dispensed by a licensed medical professional who is a member of the study team. All treatment regimens will be in accordance with standard Ugandan treatment guidelines. Study participants with positive STIs who receive treatment will also be given treatment medications to deliver to their partner(s) with the goal of preventing reinfection. This practice of patient-delivered partner medication has been shown to be efficacious in several settings, including Uganda [61].

Biologic tests; Women who initiate PrEP: Women who initiate PrEP will complete creatinine at baseline and quarterly and hepatitis B safety monitoring at baseline to ensure that there are no contraindications to using PrEP. A nurse will also assess for any symptoms experienced after initiating PrEP to evaluate for any medication side effects. Blood testing for renal function (Creatinine) and for hepatitis B infection will require 2 tubes of blood or approximately 10mL or <1 tablespoon of blood at baseline and 1 tube of blood or approximately 5mL quarterly. As per WHO guidelines, women will be eligible to initiate PrEP immediately. Women with abnormal renal function or active hepatitis B infection (HBV surface antigen positive) will be instructed to stop PrEP. Abnormal renal function will be defined as:

- Non pregnant women: serum Creatinine > 89 µmol/L and GFR < 60ml/min (Glomerular filtration will be estimated using the Cockcroft-Gault equation).

Any woman who has abnormal safety lab results will be referred to appropriate clinical care.

Adherence: Adherence of PrEP will be assessed by biological sampling as well as electronic data capture monitoring. In addition to assessing adherence we will promote adherence through offering individual adherence counselling sessions to all women who initiate PrEP at their study visits using an adherence counselling tool developed specifically for PrEP adherence.

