Plasma tenofovir testing for plasma drug level will be collected at the first visit (3 months) after PrEP initiation and at exit or incident pregnancy. TFV concentration ≥ 40 ng/mL indicates adherence in the prior 24 hours and is associated with HIV protective efficacy (1° outcome) [25, 62]. We will collect additional samples to test for phosphorylated tenofovir (TFV-DP) via dried blood spots, which are whole blood and provide longer-term exposure information (half-life 17 days). DBS samples will be analyzed to adjudicate discrepancies between Wisepill and plasma TFV levels [63, 64]. In addition, a full blood count for hematocrit/hemoglobin testing will be taken at two instances:

- At the first instance of DBS collection (for TFV levels) after the participant has initiated PrEP for the first time,
- At the time of a positive pregnancy test if the participant is on PrEP and adherence DBS labs are indicated.

This hematocrit/hemoglobin testing is a point of care test and will not require additional blood sample to be taken. The hematocrit is required to accurately interpret the TFV level in the dried blood spot which is a primary adherence outcome for the study.

For participants who have already enrolled in the project we will test hematocrit/hemoglobin at their next study visit upon re-consenting them.

Wisepill device to monitor adherence. PrEP initiators will be given a Wisepill device to measure level and patterns of adherence in real-time. Wisepill uses wireless technology to monitor medication use. Device openings are recorded and transmitted via cellular networks in real-time to the Wisepill server. While not all device openings equate to ingestion, electronic adherence monitoring provides the best-available understanding of day-to-day adherence behavior. Flash memory maintains data for later transmission if connectivity is lost. We have collected Wisepill adherence data in [name] 750-person HIV cohort in Uganda (NCT01596322) and found a high degree of acceptability, reliability and validity with respect to predicting HIV RNA rebound [65]. Outcomes (median adherence $\geq 80\%$, median adherence, and number of interruptions >72 hours) will be calculated every 28 days and summarized quarterly.

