Participants will receive a transportation refund for all study visits. This reimbursement will be determined based on the distance from the participant's home to the clinic, and can range from 10,000 UGX to 30,000 UGX. Additionally, participants will receive an incentive of 20000 Ush to compensate them for their time.

VIII. RISKS AND DISCOMFORTS: The potential risks incurred by participating in the studies include:

1. Risk of acquisition of HIV: Based on inclusion criteria, all participants will be at risk for acquiring HIV. It is therefore possible that some participants will become infected over the course of the follow-up study. All participants will be offered comprehensive counselling regarding HIV risks as well as safer conception risk. Participants will be counselled about and able to access condoms in the clinic. Women who seroconvert will be offered comprehensive HIV care at the ISS clinic.
2. Risk of developing resistant virus: Women who become acutely infected with HIV while incompletely taking TDF/FTC PrEP have an increased chance of developing resistant virus. Quarterly adherence counselling sessions will emphasize that women should come to the clinic for additional testing should she develop symptoms of acute HIV infection. Furthermore, if women adhere well, the risk of getting HIV and therefore of getting resistant virus is low.
3. Risk of partner related violence: We will promote serostatus disclosure between partners as part of our safer conception strategy. Discovery of HIV-serodiscordant status may be associated with harm to women. In addition, women who do not disclose PrEP use, may be at risk for partner-related violence should her use of this drug be discovered, given the implications that she therefore perceives herself to be at risk for HIV acquisition. In order to reduce the chance of partner violence we will facilitate referrals to couples-based HIV counselling and testing in the same space as the research is conducted.
4. Risk of Adverse effects related to taking TDF/FTC PrEP: TDF/FTC is first-line therapy in the treatment of HIV. In patients taking TDF/FTC with other HIV medicines to treat HIV infection, common side effects include: diarrhea, nausea, tiredness, headache, dizziness, depression, problems sleeping, abnormal dreams, and rash. In clinical trials of TDF/FTC as PrEP in which most people took study drug, side effects were reported by about 10% of participants (including those in the placebo group). In the Partners

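### No HIV test is written in for the PrEP initiation visit, so a woman who starts between visits could be dispensed TDF/FTC up to about 3 months after her last negative test

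*Combined protocol and SAP*

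**What the plan says.** Section V (Overview) makes women eligible to start PrEP at any time in the first 6 months of a follow-up of at most 9 months. A woman who wants to start between visits uses a "PrEP referral form to bring to the clinic if they chose to initiate PrEP outside of a scheduled study follow up visit".

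Section V (Biologic tests; All participants) sets the testing frequency: "All participants will complete quarterly urine pregnancy tests, rapid HIV tests and syndromic screening for STIs". Table 3 puts the HIV test at months 0, 3, 6 and 9/exit. The table also has a column defined as "i = PrEP initiation visit", and the HIV test is not marked there.

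For initiators, Section V (Biologic tests; Women who initiate PrEP) says: "Women who initiate PrEP will complete creatinine at baseline and quarterly and hepatitis B safety monitoring at baseline". It then allows a start without delay: "As per WHO guidelines, women will be eligible to initiate PrEP immediately". The stop rules that follow cover abnormal renal function and active hepatitis B. HIV is not mentioned in that paragraph.

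Section VIII, item 2, has counsellors advise women to come in for extra testing if symptoms of acute HIV infection appear. Section VIII, item 4, lists resistance in people with undiagnosed HIV among rare but serious effects, and says that PrEP trials had not so far reported these.

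**The concern.** The protocol builds a route for starting between visits and a table column for that visit, and it chooses which tests belong there. The test that shows whether the woman is still HIV-negative is not among them. Every participant is enrolled because she is exposed to HIV, so a result from the last quarterly visit can be out of date.

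The stake is individual safety. A woman infected since her last test could take a two-drug regimen with undiagnosed HIV until the next quarterly test. Section XIV (Analysis, Aim 1) defines initiation as collecting at least one 3-month supply, so the first dispensing can cover that whole period.

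**Working it through.** **1. Reading the schedule.** The protocol states no figure on this point, so the check starts with the rows of Table 3.

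| Row | 0 | i | 3 | 6 | 9/exit |
|---|---|---|---|---|---|
| HIV test | x | – | x | x | x |
| Creatinine | – | x | x | x | x |
| HBV serology | – | x | – | – | – |
| Adherence support | x | x | x | x | x |

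The blank is not an extraction fault. The creatinine row is empty at month 0 and filled at i, the adherence row is filled throughout, and the text of Section V agrees with the table.

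**2. Longest gap.** Scheduled tests inside the 0-6 month initiation window fall at months 0, 3 and 6. A start just before month 3 or month 6 comes just under 3 months after the last test. A start at a scheduled visit has that visit's test. No visit windows are given, so a late quarterly visit would lengthen the gap.

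**3. Size.** From the documents: 105 planned initiators (Table 4; 70% of 150) and T = 3 months = 0.25 year between tests. Assumed, because the documents give no values:
- HIV incidence r of 2-5 per 100 woman-years
- start time g spread evenly between visits
- a rapid-test window w of 0.5-1 month
- a between-visit share of 25%, with a range of 5-50%.

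*Already infected at the start:* the mean over g of 1 − exp(−r·g), which is close to r·T/2.
- r = 0.02: 0.02 × 0.125 = 0.25%.
- r = 0.05: 0.05 × 0.125 = 0.625% (0.62% exactly).
- At a 25% share there are 0.25 × 105 = 26.25 starts, so 0.07-0.16 women.

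*Caught by a same-day test:* only infections older than w are detectable.
- Fraction missed = 1 − ((3 − w)/3)². For w = 0.5 this is 31%; for w = 1 it is 56%.
- Lowest case (r = 0.02, w = 1): 0.111% × 26.25 = 0.03 women.
- Highest case (r = 0.05, w = 0.5): 0.433% × 26.25 = 0.11 women.
- Chance of catching at least one: about 3-11%.
- Over shares of 5-50% (5.25 to 52.5 starts): 0.006-0.23 women.

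*Time on PrEP before the next test, with visits kept on the enrolment calendar:*
- Women already infected at the start: ∫g(3 − g)dg ÷ ∫g dg over 0-3 = 4.5 ÷ 4.5 = 1.0 month on average.
- Women the test would catch: (3 − w)/3 = 0.67-0.83 month.

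*Extreme bound:* if all 105 initiators started at the very end of a gap, at 1-5 per 100 woman-years, the number infected would be 105 × (1 − exp(−0.25·r)) = 0.3-1.3. No realistic pattern of starts would look like this.

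**4. Effect on the outcomes.** In the 25% case, removing the women caught changes the uptake numerator by at most 0.11/150 = 0.08 percentage points. The infected women make up at most 0.16/105 = 0.15 points of the plasma tenofovir denominator. The Aim 2 comparison of HIV rates changes by well under one expected event.

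**The case against.** The strongest case against is about weight. The expected catch is a small fraction of one woman, every rate behind it is assumed, and a 5-50% range for the share amounts to saying that it is unknown. That stands, and it sets the rating.

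Table 3 is also an incomplete guide to off-calendar procedures. The STI screen is blank at i although Section V offers it at every study visit. Wisepill data are marked at month 0 and not at i, although only initiators receive the device. So the blank cell alone would be weak evidence. Here the text supplies the rest: HIV tests are quarterly, and only creatinine and hepatitis B tests are tied to initiation.

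A reader might infer that women are in fact started untested. The documents do not show this. The referral form, the WHO guidance and clinic practice are not available here, and staff may test as routine. The finding is only that the protocol does not require it.

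A reader might also take Section VIII, item 2, as direct support: "Women who become acutely infected with HIV while incompletely taking TDF/FTC PrEP have an increased chance of developing resistant virus". That sentence concerns infection acquired during PrEP use, which a test before the first dose would not prevent. The relevant hazard is the one in item 4, with the qualification the protocol attaches to it. The symptom-based advice in item 2 is not a substitute either, because it depends on symptoms and does not control dispensing.

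**Conclusion.** The point holds as a gap in the written schedule. TDF/FTC can be dispensed at a between-visit start up to about 3 months after the last negative HIV test. This is certain as a reading of the text. How often it would matter is not known.

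Under the stated assumptions the expected number of women affected is well below one. Enrolment was already under way at this version: "For participants who have already enrolled in the project we will test hematocrit/hemoglobin at their next study visit upon re-consenting them". If half of the between-visit starts remain, the expected catch falls to about 0.015-0.057 women. No resistance rate can be estimated, because the documents give none.

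The documents do not support reading this as a threat to the uptake or adherence estimates, or as a problem for every initiator. It is a low-cost safety correction of minor expected size.

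**What to change.** Mark the rapid HIV test in the initiation column of Table 3. In Section V (Biologic tests; Women who initiate PrEP), add one sentence: at any start outside a scheduled visit, a negative rapid HIV test on the same day is required before PrEP is dispensed. The gap since the last test then falls from about 3 months to zero.

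The cost is about 5-53 extra finger-pricks (5-50% of 105 initiators). These women are already giving blood, at a clinic that runs the test and describes it as "waiting approximately 10-20 minutes for results", so immediate starts remain possible. The change also needs an amendment through the two ethics committees named in Section XII. It may need re-consent, as the added hematocrit test did, although quarterly HIV testing is already a study procedure. Under the assumed window the test would still miss about 31-56% of infections present at the start, so the quarterly test must continue. No change to the sample size, the outcomes or the analysis is needed.

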For the duration of the study, enrolled women will be under the care of [name] [name] who is the clinician for the study. Women will be expressly counselled on when and how to contact [name] [name] throughout the duration of their participation. [name] [name] and other study staff will be available to participants between their study visits to discuss potential symptoms or problems.

XII. MANAGEMENT OF ADVERSE EVENTS:

Adverse events and serious adverse events will be assessed and logged by study staff at each study visit. Unanticipated adverse events reported to the clinic staff or study clinician outside of normal study visits will be recorded and participants will be referred to appropriate care. All adverse events will be reviewed by the Principal Investigators and other relevant study/clinical staff and reported to appropriate study ethics committees (MUST IRB, Partners Healthcare IRB).

XIII. POST STUDY ACCESS TO TDF/FTC

PrEP is not currently provided in the public sector in Uganda. We will inform exiting participants about their options for accessing it in the private sector, or, should it become available, in the public sector.

XIV. BIOSTATISTICAL ANALYSIS

Analysis, Aim 1

Hypothesis: 70% of women will initiate PrEP as part of a safer conception strategy. In the Partners PrEP demonstration project, PrEP uptake is ~90% among uninfected women in mutually-disclosed serodiscordant partnerships ([name], personal communication). We expect uptake to be lower among women who are not in mutually-disclosed serodiscordant partnerships and who may worry about the effects of PrEP on pregnancy. We hypothesize that PrEP uptake will be associated with relationship power and social support.

Table 4. 95% CIs for range of uptake and adherence.		
% uptake or adherence	Uptake, N = 150 95% CI	Adherence ¹ , N = 105 95% CI
50	42.5-57.5%	40.4-59.6%
60	52.6-67.4%	50.6-69.4%
70	63.1-76.9%	61.2-78.8%
80	74.0-86.0%	72.3-87.7%
90	85.5-94.5%	84.3-95.7%
1. Detectable drug at visit 3 months after initiation		

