Estimates of PrEP uptake: PrEP uptake/initiation is defined as the proportion of enrolled women who collect at least one 3-month supply of PrEP. A target sample size of 150 women produces a 95% CI width between 13% (when 70% initiate PrEP) and 15% (when 50% initiate PrEP) (Table 4.) We will calculate the prevalence (and 95% CI) of PrEP initiation using an intercept-only logistic regression model to account for potential clustering within the two groups (women enrolled through partners, women enrolled as individuals). We will describe, compare and test for differences between baseline characteristics of women who do and do not initiate PrEP. Log binomial regression with GEE will be used to estimate univariable and multivariable-adjusted risk ratios (RR) and 95% CIs for the associations between relationship power/social support and PrEP initiation. We will assess potential confounding factors individually; any factor with $P \geq 0.20$ will be excluded from further consideration and the remaining covariates entered into a multivariable model.

Analysis, Aim 2

Hypothesis: 70% of women will have detectable drug 3 months after PrEP initiation.

Estimates of periconception PrEP adherence:

Periconception PrEP adherence will be defined as PrEP initiators with plasma TFV concentration $\geq 40\text{ng/mL}$ three months after initiating PrEP. A target sample size of 105 women initiating PrEP will provide 95% CI width of 18% when

the percent of high adherers is 80% (Table 4). Secondary adherence outcomes are based on Wisepill device monitoring. We will determine the mean and median number of pills taken as well as patterns of adherence (gaps). We will consider Wisepill adherence as a binary outcome defined as taking $\geq 80\%$ of prescribed doses based on biologic plausibility and prior studies [23, 65, 71, 72]. Monthly assessments of median (interquartile range) adherence and number of 72-hour adherence gaps will be used to examine longitudinal trends in adherence.

We will calculate prevalence (and 95%CI) of PrEP adherence using an intercept-only logistic regression model with GEE. Log binomial regression with GEE will be used to estimate univariable and multivariable-adjusted risk ratios (RR) and 95% CIs for the associations between relationship power/social support and PrEP adherence.

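### The primary 3-month adherence proportion is defined over PrEP initiators but needs an attended blood draw, and the plan has no rule for initiators without a sample

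*Combined protocol and SAP*

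**What the plan says.** - **Who counts as an initiator.** Section XIV, Analysis Aim 1, defines uptake as "the proportion of enrolled women who collect at least one 3-month supply of PrEP". A woman who takes her first supply home and never returns is therefore an initiator.
- **The outcome.** Analysis Aim 2 states: "Periconception PrEP adherence will be defined as PrEP initiators with plasma TFV concentration" of at least 40 ng/mL three months after starting. Section V marks this as the primary outcome. The footnote to Table 4 reads "Detectable drug at visit 3 months after initiation".
- **When plasma is taken.** Section V says that it "will be collected at the first visit (3 months) after PrEP initiation and at exit or incident pregnancy". Table 3 lists drug-level testing at months 3, 6 and 9/exit for women who start PrEP.
- **Planned numbers.** Aim 1 has "Hypothesis: 70% of women will initiate PrEP as part of a safer conception strategy", and Aim 2 has "Hypothesis: 70% of women will have detectable drug 3 months after PrEP initiation". The adherence column of Table 4 uses N = 105.
- **Estimator.** Aim 2 names an intercept-only logistic model with GEE. It gives no rule for missing results, no allowance for dropout and no sensitivity analysis. Section XV lists retention only as an item for periodic review.
- **Wisepill.** Section V says: "Device openings are recorded and transmitted via cellular networks in real-time to the Wisepill server". Aim 2 makes Wisepill adherence of at least 80% a secondary outcome. Dried blood spots are to settle disagreements between Wisepill and plasma, but they too need a visit.

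**The concern.** The definition names one group (initiators), while the measurement exists only for a smaller one (initiators who attend). The plan does not connect the two. A logistic GEE as ordinarily fitted drops records with no outcome, so a literal run of the plan gives the proportion among women sampled. If women who stopped taking PrEP are also less likely to return, the missing results fall mainly among the non-adherent and the estimate is too high. The confidence interval would not show it, because it reflects sampling error only.

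The figure at stake is the one to be compared with the hypothesised 70%. The study will already hold remote information on pill-device use by women who did not return, but nothing in the plan uses it to inform a missing plasma result.

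**Working it through.** **1. Reproduce Table 4.** Inputs: uptake 70% and 150 women (Aim 1), so 0.70 × 150 = 105 initiators. The Wald interval is p ± 1.96 × √(p(1−p)/n). At p = 0.70 and n = 105 the half-width is 1.96 × √(0.21/105) = 0.088, giving 61.2% to 78.8%, as printed. The other four adherence rows also reproduce at n = 105. The stated precision therefore assumes a result for every expected initiator.

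**2. Loss of precision.** Assume 10% of samples are missing: n = 0.9 × 105 = 94.5, and the half-width is 1.96 × √(0.21/94.5) = 0.092, or 9.2 points instead of 8.8. This is a small loss.

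**3. Possible bias, extreme case.** Let m be the share of initiators without a sample. If true adherence over all initiators is 70% and no missing woman is adherent, the samples-only estimate is 0.70/(1 − m). The values of m are assumptions.

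| m | samples-only estimate | bias (points) |
|---|---|---|
| 5% | 73.7% | 3.7 |
| 10% | 77.8% | 7.8 |
| 11% | 78.7% | 8.7 |
| 20% | 87.5% | 17.5 |

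So about 11% missing shifts the estimate by roughly Table 4's half-width. From a lower starting point, true adherence of 60% with 15% missing reads 0.60/0.85 = 70.6%, close to the hypothesised value.

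**4. Possible bias, mixed case.** Assume true adherence of 70%, with samples missing for 5% of adherent and 25% of non-adherent women.

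- Sampled and adherent: 0.70 × 0.95 = 0.665. Sampled and not adherent: 0.30 × 0.75 = 0.225. Missing: 0.035 + 0.075 = 0.11.
- Samples only: 0.665/0.890 = 74.7%.
- Missing counted as not adherent: 66.5%.
- Missing counted as adherent: 0.665 + 0.11 = 77.5%.
- Imputed from Wisepill, assuming that the device shows use for 85% of adherent and 15% of non-adherent women. Among sampled women, the probability of adherence is 0.565/0.599 = 0.944 if use is shown and 0.100/0.291 = 0.343 if not. Of the missing, 0.041 show use and 0.069 do not. The estimate is 0.665 + 0.041 × 0.944 + 0.069 × 0.343 = 72.7%.

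The truth (70%) lies between 66.5% and 77.5%. Imputation removes 2.0 of the 4.7 points of bias and leaves 2.7. The 85%/15% rates have no source in the documents.

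**5. Bounds from an observed result.** If 70% of sampled women are adherent, the all-initiator proportion lies between 0.70(1 − m) and 0.70(1 − m) + m: 66.5% to 71.5% at m = 5%, 63.0% to 73.0% at 10%, and 56.0% to 76.0% at 20%. The lower bound passes below Table 4's lower limit once m exceeds 1 − 61.2/70 = 12.6%.

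**The case against.** A reader might infer that the plan excludes unsampled women and that adherence will therefore be overstated. The text does not go that far. The outcome is worded over initiators, and the sample size is stated for initiators: "A target sample size of 105 women initiating PrEP will provide 95% CI width of 18% when" (the 18-point width fits the 70% row of Table 4, not the 80% row that the sentence goes on to name, which is a separate slip). The same model runs equally well with missing results coded as not adherent, which would not overstate adherence. This stands: exclusion is what the named model does by default, not a stated rule.

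A reader might also infer that the Wisepill data on non-returners go to waste. They do not. Wisepill adherence is a planned secondary outcome for initiators, with its own 70% hypothesis in Section II. It is only not used to inform missing plasma results.

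Other points lower the likely size. Plasma is also due at exit in general, not only at pregnancy. Women who stop PrEP stay in follow-up, with quarterly tests, a transport refund and a payment for time. Eligibility requires residence within 60 km of the clinic. A woman who misses month 3 may give a level later, although the plan does not say whether it may stand in. All of this may keep missingness low. None of it says what to do with a missing result, and a woman who starts at month 6 has only one scheduled visit left.

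Finally, this is a descriptive single-cohort study with no decision rule tied to 70%. That limits the consequences but does not remove the need for a defined denominator.

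**Conclusion.** The concern holds as a gap in the primary Aim 2 analysis. The outcome depends on attendance, the group is all initiators, and the treatment of initiators without a sample is left open. Run by its ordinary default, the named model would overstate adherence provided that non-returners are less adherent than returners. That is plausible, but the documents do not establish it.

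The size cannot be taken from the documents. At an assumed 11% missing and true adherence of 70%, the bias is 4.7 points in the mixed case and about 9 points if no missing woman is adherent. The larger figure is a worst case, and the 87.5% at 20% missing requires two-thirds of all non-adherent women to be missing (20 of 30 points) and no adherent woman. The choice of rule alone moves the mixed-case figure from 74.7% to 66.5%.

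The samples-only estimate should not be presented as an upper bound: if missing women were more adherent than those sampled, the truth would lie above it.

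**What to change.** In Section XIV, Analysis Aim 2, before analysis:

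1. State that the denominator is all PrEP initiators, and say whether a sample taken later, at exit or at incident pregnancy may stand in for the 3-month result.
2. Report the proportion with missing counted as not adherent (lower bound) beside the samples-only estimate, and give the proportion with missing counted as adherent as the strict upper bound. Report the number missing.
3. Add an estimate that multiply imputes missing 3-month TFV from the Wisepill openings before the due date plus baseline covariates. Say that an opening does not always mean ingestion, that a silent device may reflect a fault, and that imputation is expected to remove only part of the bias.
4. Note under Table 4 that N = 105 assumes no missing sample. At an assumed 10% missing, about 94 results remain and the half-width at 70% is 9.2 rather than 8.8 points.

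This needs SAP wording and a few lines of code, with no new data collection. The cost is a little more analysis and a slightly less favourable headline figure.
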